**Schedule of Control Arm Subject Follow-up and Visit Windows**

Follow-up Visit Interval	Follow-up Visit Interval Window
1 month	1 month (30 days) $\pm$ 2 weeks (14 days)
6 months	6 months (182 days) $\pm$ 1 month (30 days)
12 months	12 months (365 days) $\pm$ 2 months (60 days)
18 months	18 months (547 days) $\pm$ 2 months (60 days)
24 months	24 months (730 days) $\pm$ 2 months (60 days)
Year 3	36 months (1,095 days) $\pm$ 2 months (60 days)
Year 4	48 months (1,460 days) $\pm$ 2 months (60 days)
Year 5	60 months (1,825 days) $\pm$ 4 months (120 days)

CONFIDENTIAL INFORMATION

MD133254 Statistical Analysis Plan Template

Revision# 1

Doc Type: GC

### ***3.3 Data and Safety Monitoring Board***

An independent Data and Safety Monitoring Board (DSMB) will be comprised of an interdisciplinary team of five individuals, four physicians and a biostatistician, who are not directly involved in the conduct of the study.

The team shall include, at minimum, one stroke neurologist, one interventional cardiologist, and a biostatistician to assist with formulation of stopping rules and direction of interim analyses.

The members may be compensated for their participation in the DSMB, including reimbursement for reasonable travel expenses to attend meetings. Members will not have any business or financial affiliation with the study sponsor, the core laboratories, or the study investigators.

The DSMB is responsible for conducting periodic reviews of aggregate data on a prescribed schedule. Based on the safety data, the DSMB will make recommendations to the Sponsor. Recommendations may include modifying the study, stopping the study, or continuing the study. All final decisions regarding study modifications or study continuation, however, will rest with the Sponsor.

### ***3.4 Clinical Events Committee***

The independent Clinical Events Committee (CEC) will be comprised of at least three physicians who are not participating in the study and do not have any conflicts of interest with the study Sponsor. The CEC will include representatives from at least three of the following specialties/disciplines:

- stroke neurology
- interventional cardiology
- echocardiography
- neuroradiology

Input from other disciplines will be solicited, if required. The members may be compensated for their involvement in the CEC including reimbursement for reasonable travel expenses to attend meetings.

The committee will be responsible for:

- Review of definitions of clinical endpoints in the study in conjunction with the Sponsor.
- Review and adjudication of adverse events that have the potential to be study endpoint events, including death, stroke, and TIA; AND
- Subsequent classification of these adverse events as related to the study device, procedure, or medications.

### ***3.5 Site Enrollment Restrictions***

There is no per-site subject enrollment limit specified for this study.

### ***3.6 Core Labs***

An independent MRI Core Laboratory will provide centralized assessment of study endpoints from protocol-required MRI and CT imagery. Three board-certified radiologists with specific neurological

**CONFIDENTIAL INFORMATION**

MD133254 Statistical Analysis Plan Template

Revision#: 1

Doc Type: GC

imaging expertise will be responsible for the review of all MRI and CT images. The principal measures provided by this core lab are detection of new brain infarct from screening to 24 months for the brain infarct endpoint, and detection of brain infarct for the recurrent event endpoint, especially regarding confirmation of a TIA as a recurrent event. The core lab readers are blinded to treatment in their image assessments.

Similarly, an independent Echocardiography Core Laboratory will provide centralized assessment of study endpoints from protocol-required echocardiography imagery, principally to confirm the presence of PFO in all subjects and to assess PFO closure status at follow-up for test subjects. Three board-certified cardiologists with expertise in echocardiography will be responsible for the review of all echocardiograms.

Refer to Section 3.19, Imaging Analysis, in the protocol.

## 4.0 Statistical Analyses and Methods

### 4.1 Analysis Sets

The co-primary endpoints will be analyzed under several different analysis set definitions, as described below. The primary analysis set for testing of the co-primary endpoints is the intent-to-treat analysis set.

#### 4.1.1 Intent-To-Treat (ITT) Analysis Set (Primary Analysis Set)

The ITT analysis set is defined as all enrolled subjects (randomized to treatment) and will be analyzed by treatment assigned at randomization, regardless of whether or not the correct treatment was administered.

#### 4.1.2 Per-Protocol Analysis Set

For per-protocol analysis, only subjects who were randomized and treated according to protocol will be analyzed by treatment assigned at randomization. Specifically, subjects randomized to test who received antiplatelet medical therapy and PFO closure with the test device, and subjects randomized to control who received antiplatelet medical therapy and no PFO closure by any means, will be included in the analysis.

#### 4.1.3 As-Treated Analysis Set

For as-treated analysis, subjects who were randomized and treated will be analyzed by treatment received, regardless of treatment assigned at randomization. Specifically, randomized subjects who received antiplatelet medical therapy and PFO closure by any means (test device, alternative device, surgery) will be analyzed in the “PFO Closure” group, and randomized subjects who received antiplatelet medical therapy and no PFO closure by any means will be analyzed in the “No PFO Closure” group.

CONFIDENTIAL INFORMATION

MD133254 Statistical Analysis Plan Template

Revision# 1

Doc Type: GC

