3.7. Randomization and Enrollment

Upon completion of screening tests and confirmation of study eligibility, consented patients will be **randomized** to a treatment arm. Using the EDC database approved by the Sponsor, the patient will be assigned to a treatment arm in the study. Patients will have a 2-in-3 chance of being randomized to the test (device) arm.

Because of the inclusion criteria of prior cryptogenic stroke, patients may have already initiated antiplatelet medical therapy prior to randomization. All patients will be instructed to continue antiplatelet medical therapy or begin antiplatelet medical therapy, according to the regimen prescribed in this protocol and upon instruction of their Neurologist Investigator.

For all patients randomized, if the subject has already initiated antiplatelet medical therapy prior to randomization, treatment should continue based on the antiplatelet regimen prescribed in this protocol (see Section 3.9 – Initiation and Administration of Antiplatelet Therapy). If antiplatelet medical therapy is not in progress or a regimen change is required, treatment should commence promptly (within 48 hours of randomization).

Patients randomized to the test (device) arm must be treated (have a PFO closure attempt) **within 90 days** of randomization.

Patients are considered "**subjects**" enrolled in the study following randomization to a treatment arm. A patient is considered **enrolled** into the clinical study when:

- he/she signs the consent form, and
- he/she completes all required screening tests and evaluations, and
- he/she meets inclusion/exclusion criteria, and
- he/she is randomized to a treatment arm.

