3.10.4. Procedure

Subjects will undergo percutaneous transcatheter PFO closure with the GORE[®] HELEX[®] Septal Occluder / GORE[®] CARDIOFORM Septal Occluder (or alternative closure method if closure with the GORE[®] HELEX[®] Septal Occluder / GORE[®] CARDIOFORM Septal Occluder cannot be achieved). The procedure starts upon venous cannulation and the procedure ends upon removal of the final catheter. Procedure start and stop times will be recorded for this study.

Anesthesia times, whether general anesthesia or conscious sedation, and fluoroscopy times will be recorded during the procedure. Anesthesia starts when the subject is intubated and stops when the subject is extubated. Sedation starts at the time of intravenous (IV) administration and stops when the subject becomes responsive (or termination of subject monitoring). Fluoroscopy time is the total fluoroscopy exposure time recorded during the procedure.

The Investigator should follow the Instructions for Use (IFU) of the GORE[®] HELEX[®] Septal Occluder / GORE[®] CARDIOFORM Septal Occluder (see Appendix E: Instructions for Use) when performing this procedure. (Note: Protamine is not to be given to reverse heparin).

Subjects who have a delivery attempt with the GORE[®] HELEX[®] Septal Occluder / GORE[®] CARDIOFORM Septal Occluder but whose PFO cannot be closed with the device (e.g., closed with an alternative occluder device, surgery, or no closure) will be considered technical failures. Subjects who are technical failures will remain in the study and should be followed per the protocol based on the original treatment assignment received (reference Section 3.16 Treatment Changes Post-Randomization).

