3.16. Treatment Changes Post-Randomization

If a subject is randomized to a treatment arm, but receives the alternative treatment during the course of the study, every effort should be made to follow those subjects according to their original treatment arm schedule.

If a subject in the control arm receives PFO closure during the course of the study the Intervention CRF should be completed to document the procedure. Additional follow-up visits may be conducted per standard of care at the given investigational site.

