### 2.4 Study Treatment Arms

#### 2.4.1 Test Arm and Test Device

The test arm will consist of enrolled subjects who were determined by the randomization process to receive the test treatment regimen, which consists of prompt antiplatelet medical therapy and PFO closure with the test device within 90 days of randomization. At the start of enrollment in December 2008, the test device was the GORE® HELEX® Septal Occluder; with Protocol Amendment 2, dated May 15, 2012, the test device was changed to the GORE® CARDIOFORM Septal Occluder.

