### 2.5 Study Endpoints

#### 2.5.1 Primary Endpoints

Co-primary Endpoint 1 is freedom from a recurrent stroke or imaging-confirmed TIA through at least 24 months post-randomization. For this study, a **recurrent stroke or imaging-confirmed TIA event** is defined as the first occurrence, post-randomization, of one of the following:

- Clinical finding of ischemic stroke that may be associated with MRI evidence of a new relevant brain infarction. For this study, an ischemic stroke is defined as a neurological deficit, presumed due to ischemia, persisting longer than 24 hours or until death.
- Clinical finding of TIA that also has MRI evidence of a new relevant brain infarction. For this study, a TIA is defined as a transient neurological deficit, presumed due to ischemia, persisting less than 24 hours.

Co-primary Endpoint 1 will be calculated as the time from randomization to the first recurrent event. Subjects free from a recurrent event will be censored at the date of last known contact.

All deaths and suspected recurrent stroke/TIA events will be reviewed and adjudicated by a Clinical Events Committee (CEC). In the event of subject death, all possible efforts will be made to obtain relevant records from the hospital or the subject's primary care physician, including a death certificate or autopsy report, to determine the cause of death.

Co-primary Endpoint 2 is the incidence of subjects with new brain infarct or stroke from screening through 24 months or last follow-up visit, whichever occurs first, hereinafter referred to as **brain infarct**. A responder is defined as any subject with at least one new T2 hyperintense MRI lesion with diameter  $\geq 3$  mm from screening or clinical findings of ischemic stroke, through 24 months or last follow-up visit, whichever occurs first. It will be calculated as a subject-based binomial proportion.

CONFIDENTIAL INFORMATION

MD133254 Statistical Analysis Plan Template

Revision#: 1

Doc Type: GC

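### The as-treated and per-protocol sets sort subjects by whether closure ever happened, while Endpoint 1 time starts at randomization, so these supportive estimates carry a timing error

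*SAP*

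**What the plan says.** SAP 4.1 makes ITT the primary analysis set and says both co-primary endpoints will also be analyzed under the other sets.

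- **As-treated (SAP 4.1.3).** The closure group holds randomized subjects "who received antiplatelet medical therapy and PFO closure by any means (test device, alternative device, surgery"). Those with no closure of any kind form the other group.
- **Per-protocol (SAP 4.1.2).** The set keeps "subjects randomized to test who received antiplatelet medical therapy and PFO closure with the test device" and drops any control who was closed.
- **Time origin (SAP 2.5.1).** "Co-primary Endpoint 1 will be calculated as the time from randomization to the first recurrent event". Event-free subjects are censored at last known contact.
- **Closure in the test arm.** SAP 2.4.1 plans "PFO closure with the test device within 90 days of randomization". Protocol 3.7 reads "Patients randomized to the test (device) arm must be treated (have a PFO closure attempt") within that period and makes no exception for a subject who has had an event. Protocol 3.10.4 adds that "Subjects who are technical failures will remain in the study".
- **Closure in a control.** Protocol 3.16 provides for it without a time limit: "If a subject in the control arm receives PFO closure during the course of the study", the Intervention CRF is completed.

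Neither SAP section gives a closure date rule, a landmark, censoring at crossover, or a rule for a closure that follows an endpoint event.

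**The concern.** Group membership is fixed at time zero by something that happens later and that an early event can influence. A test subject who has a stroke in week 3 and is then never closed counts in the no-closure group as-treated, and disappears per-protocol. A control who stays event-free for a year and is then closed brings that event-free year into the closure group. A control closed after an event would carry the event into the closure group.

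These are the sets the SAP names for looking at treatment actually received. The regional, worst-case, best-case and tipping-point analyses in SAP 4.8 and 4.10 do not group by closure. If the as-treated result differs from ITT, a reader cannot tell how much of the difference comes from the sorting rule.

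**Working it through.** The documents give no figure for these sets, so there is none to reproduce.

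**Inputs from the documents.** 443 test and 221 control subjects (Protocol 3.3); 92% event-free at 24 months, range 86-94% (SAP 2.7.1); closure within 90 days (SAP 2.4.1); analysis when the last subject reaches 24 months, with data through 5 years (SAP 4.2.1, 4.3.1).

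**Assumptions.** Closure is spread evenly over 0-90 days (mean 1.5 months), the hazard is constant and there is no dropout. Crossover, prevention of closure and post-event closure are varied.

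**1. Test-arm events before closure.** Monthly hazard = -ln(0.92)/24 = 0.003474. Expected events = 443 × (1 - exp(-0.003474 × 1.5)) = 2.3. At 86% event-free this is 4.2.

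**2. Moving them by hand, true HR 1.** Simulated follow-up gives about 72 test and 36 control events. The moved subjects contribute little follow-up, so person-time is taken as proportional to 443 and 221.

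- As-treated: [(72 - 2.3)/443] / [(36 + 2.3)/221] = 0.91.
- Per-protocol: [(72 - 2.3)/443] / [36/221] = 0.97.
- The standard error of log HR is about √(1/72 + 1/36) = 0.20, so ln(0.908) = -0.097 is roughly half a standard error.

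**3. The opposite case.** Suppose closure is recorded after 10% of control events (3.6) and all test subjects are closed.

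- As-treated: [(72 + 3.6)/443] / [(36 - 3.6)/221] = 1.16.
- Per-protocol: [72/443] / [32.4/221] = 1.11.

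**4. Simulation, true HR 1.** A range shows two simulations. One confines crossover to the first two years; the other sets 10% by 24 months.

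| Scenario | As-treated HR | Per-protocol HR |
|---|---|---|
| Early event always prevents test closure, no crossover | 0.90-0.92 | 0.96-0.98 |
| Early event prevents closure half the time | 0.96 | 0.99 |
| All test subjects closed, no crossover | 0.99-1.01 | 0.99-1.01 |
| All test subjects closed, 10% event-free control crossover | 0.86-0.97 | 0.90-0.98 |
| Always prevents, 10% crossover | 0.88 | 0.95 |
| Same, plus 4% of test subjects never closed | 0.79 | 0.87 |
| Closure recorded after 10% of control events, all test subjects closed | 1.16 | 1.11 |

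In the first row the as-treated comparison rejects one-sided at 0.025 in 7.2% of trials, against 2.5-2.9% for ITT. With closure within 30 days the as-treated HR is 0.96-0.97. With a threefold hazard in the first three months it is 0.78. If half of control events were followed by a recorded closure it would be 2.32.

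**5. Time-dependent closure status.** With true HR 1 it returns 0.99-1.01 wherever closure timing is unrelated to prognosis. With true HR 0.45 and early events preventing closure it returns 0.45, where as-treated gives 0.41 and per-protocol 0.44. If half the subjects have four times the hazard and three times the crossover rate, it returns 1.08 or 1.17 under no effect (base crossover 10% or 20%).

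**6. Endpoint 2, no true difference, 8% clinical events, early event prevents closure.** Expected responders are 35.4 test and 17.7 control. As-treated: (17.7 + 2.3)/(221 + 2.3) - (35.4 - 2.3)/(443 - 2.3) = 8.95% - 7.52% = 1.4 points toward the device. Per-protocol: 8.00% - 7.52% = 0.5 points.

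**The case against.** **Only supportive.** SAP 4.1 makes ITT primary, and nothing in SAP 4.1 to 4.1.3 gives the other sets a decision role. This stands, and it limits the point to an improvement of secondary results.

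**Possibly no error at all.** Protocol 3.7 requires a closure attempt whether or not an event has occurred, and SAP 2.4.2 describes controls as not closed. If both held without exception the as-treated HR would be about 1.0. That is true, but Protocol 3.10.4 and 3.16 plan for failures and crossovers, so the sets need a rule for them.

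**The upward direction is thin.** A reader might infer from the 1.16 that the set could as easily lean against the device. The documents make this less likely. Protocol 3.14 follows controls until recurrent stroke or imaging-confirmed TIA, and Protocol 3.17 requires no follow-up after a confirmed event. It is not excluded: Protocol Table 8 asks for the completion form only for MRI-confirmed events, an Endpoint 1 stroke need not be MRI-confirmed, and SAP 4.1.3 does not bar later closures.

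**The rule may sit elsewhere.** SAP 5.1 leaves calculation logic to dataset specifications that are not available here. The point is therefore limited to the SAP and protocol text, which is where set membership should be defined.

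**Conclusion.** The gap is in the text: membership in both sets depends on a later closure, with no ordering or censoring rule. The ITT test is unaffected. For the supportive estimates the shift is modest in the simplest case (as-treated HR 0.90-0.92 under no effect, about half a standard error) and can be zero, larger or reversed under other facts. Per-protocol is usually less affected, but not always: with 4% of test subjects unclosed, 5% crossover and closure after 20% of control events it gives 1.12 against 1.10 as-treated.

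Three stronger readings are not supported.

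- The figures do not bound the error. Delay, crossover, prevention and post-event closure rates are all assumed, because the documents give none.
- The error does not always favor the device.
- Time-dependent coding does not turn the as-treated result into a causal effect of closure. It removes the timing error only; who gets closed can still be related to risk, as the 1.08 and 1.17 show.

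**What to change.** **SAP 4.1.3, Endpoint 1.** Replace the fixed grouping with a Cox model in which closure status is 0 from randomization and 1 from the closure date. Ignore a closure after the first endpoint event. Count an event on the procedure date as exposed, and say so: if 0.5% of test subjects (2.2) had a procedure-day stroke, the null HR would be 1.06 counted as exposed and 0.97 counted as unexposed. State that the model does not remove confounding and that the result stays supportive.

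**SAP 4.1.2, Endpoint 1.** Include controls who cross over and censor them at closure. Ignore a control closure that follows an event. Do not exclude a test subject because an endpoint event came before closure within the 90-day window. State that censoring at crossover is assumed non-informative.

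**Endpoint 2.** The endpoint is binary and a silent infarct has no onset date, so the Cox model does not carry over. State that a closure after the endpoint event does not change a subject's group, keep the test-device condition in the per-protocol set, and report the as-treated result as descriptive. This settles the ordering but does not remove the shift in step 6, hence the label. A grouping by status at day 90 is not recommended: it would count some never-closed test subjects as closed, and with 10% non-closure it leaves 0.22-0.27 points in the as-treated comparison.

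**Cost.** A few sentences and start-stop coding. The dates are already collected: "Procedure start and stop times will be recorded for this study", and control closures go on the Intervention CRF. The downsides are slightly more programming, a censoring assumption, and possibly less favorable supportive estimates. The SAP is dated January 2016 and enrollment was completed in February 2015, so the rules could be set before the last subject's 24-month visit.

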## 4.2 *Timing of Analyses*

### 4.2.1 Primary Endpoint Analysis

The primary endpoint analysis will be performed when the last subject enrolled completes 24 months of follow-up.

### 4.2.2 Interim Analyses

The original protocol specified that, in addition to standard study monitoring, an interim analysis will be performed after approximately 50% of the total expected recurrent stroke or imaging-confirmed TIA events have occurred. This milestone event had not occurred as of the completion of full enrollment in February 2015. Under the plan described herein, the original interim analysis plan no longer serves its purpose and is rescinded.

## 4.3 *Primary Endpoints*

### 4.3.1 Freedom From Recurrent Event

Co-primary Endpoint 1, freedom from a recurrent event, will be compared between treatment groups using an unadjusted log-rank test and presented using Kaplan-Meier methods. All follow-up data through 5 years will be included on subjects continuing follow-up past the 24-month evaluation. As part of a simultaneous test with the brain infarct co-primary endpoint hypothesis (described in sections 4.3.2 and 4.5 below) a multiplicity-adjusted p-value for the hazard ratio test of 0.025 or less will be considered evidence to reject the freedom from recurrent event null hypothesis.

### 4.3.2 Brain Infarct

The analysis sample for Co-primary Endpoint 2, brain infarct, will consist of randomized subjects with valid MRI Core Lab data at screening and an appropriate follow-up, where follow-up will be at 24 months or immediately following a recurrent event (suspected stroke or TIA), whichever occurs first, as well as randomized subjects who experience a confirmed recurrent event through 24 months regardless of MRI data status. Responders are subjects who show one or more new infarction(s) on MRI since screening or experience a confirmed recurrent event. Nonresponders are subjects who do not show new infarction on MRI since screening and do not experience a confirmed recurrent event.

The primary analysis will be a two-sample comparison of the binomial proportion of subjects with brain infarct between the two treatment groups. Each binomial proportion will be calculated as the count of responders divided by the count of evaluable subjects (sum of the responder and nonresponder counts).

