2.8. Statistical Analysis of Primary Endpoints

The primary endpoint analyses will be performed when the last subject enrolled completes 24 months of follow-up.

Co-primary Endpoint 1, freedom from a recurrent event, will be compared between treatment groups using an unadjusted log-rank test and presented using Kaplan-Meier methods. All follow-up data through 5 years will be included on subjects continuing follow-up past the 24-month evaluation. As part of a simultaneous test with the brain infarct co-primary endpoint hypothesis a multiplicity-adjusted p-value for the hazard ratio test of 0.025 or less will be considered evidence to reject the freedom from recurrent event null hypothesis.

The analysis sample will consist of randomized subjects with valid MRI core lab data at screening and an appropriate follow-up, where follow-up will be at 24 months or immediately following a recurrent event (suspected stroke or TIA), whichever occurs first, as well as randomized subjects who experience a confirmed recurrent event through 24 months regardless of MRI data status. Responders are subjects who show one or more new infarction(s) on MRI since screening or experience a confirmed recurrent event. Nonresponders are subjects who do not show new infarction on MRI since screening and do not experience a confirmed recurrent event.

The primary analysis will be a two-sample comparison of the binomial proportion of subjects with brain infarct between the two treatment groups. Each binomial proportion will be calculated as the count of responders divided by the count of evaluable subjects (sum of the responder and nonresponder counts).

The hypothesis will be tested using a two-sample binomial proportions test:

$$z = \frac{p_C - p_T}{\sqrt{\frac{p_C(1 - p_C)}{n_C} + \frac{p_T(1 - p_T)}{n_T}}}$$

where:

- p_{C} = observed brain infarct proportion in control group
- $n_{\mathcal{C}}$ = number of evaluable subjects in control group
- p_T = observed brain infarct proportion in test group
- n_T = number of evaluable subjects in test group

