3.18. Subject Withdrawal or Discontinuation from the Clinical Study

The Investigator should encourage subjects to return for the required follow-up visits. These measures are important as the clinical study objectives may not be realized if a large number of subjects are lost to follow-up (LTF).

A subject may withdraw from the clinical study at any time and should notify the Investigator in this event. If a subject refuses to return for the follow-up visits, the Investigator will attempt to obtain at least vital status and complete the Stroke-Free Questionnaire. If the Stroke-Free Questionnaire suggests a possible event, then records and images will be requested for adjudication in the same manner as all suspected endpoints. In the event of subject death, a death certificate or autopsy report should be obtained to confirm cause of death and reported on the Subject Completion / Discontinuation Form.

A subject will be considered lost to follow-up and discontinued from the study when both of the following criteria have been met: the subject has missed two consecutive follow-up visits, and the Investigator has documented three failed attempts to contact the subject. One of the three documented attempts must include a certified (traceable) letter. The Investigator will ensure that the appropriate CRF (Study Completion / Discontinuation Form) is completed, documenting the subject's discontinuation (*i.e.*, lost to follow-up) from the clinical study. If a subject is considered lost to follow-up, the Investigator will attempt to obtain vital status and complete the Stroke-Free Questionnaire annually from the point of last contact. Any information collected after the time of discontinuation should be captured in the study database under an Unscheduled visit.

The Investigator may also withdraw the subject from the clinical study at any time based on the Investigator's medical judgment.

The study Monitor will ensure that subject withdrawals are documented properly, discussed with the Investigator, and reported to the Sponsor (ISO 14155 – 1:2003, Section 9.1(j.).

- 3.19. Imaging Analysis
 - 3.19.1. MRI / CT

For all subjects, an independent MRI Core Laboratory will compare the screening MRI with the 24 month follow-up or recurrent event MRI for a determination of study imaging endpoints.

Variables assessed by the MRI Core Laboratory will include:

- Screening lesion evaluation
- Change in focal lesion on follow-up scan

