#### 4.10 Additional Analyses

Additional subgroup analyses may be performed based on variables identified to be significant predictors ( $p$ -value  $< 0.05$ ) in multivariate analyses.

Sensitivity analyses of the recurrent event and brain infarct co-primary endpoints will be conducted and will include, at a minimum, a “worst-case” analysis (subjects who withdraw or are lost to follow-up considered recurrent events in the test group and censored in the control group), a “best-case” analysis (subjects who withdraw or are lost to follow-up considered censored in the test group and recurrent events in the control group), and, if necessary, a tipping point analysis (threshold of successes vs. failures between the treatment groups at which the primary test conclusion changes).

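### Brain infarct is tested in evaluable subjects rather than the declared ITT set, and no required analysis examines followed, event-free subjects without usable imaging

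*SAP*

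**What the plan says.** **Declared set.** SAP 4.1 states: "The primary analysis set for testing of the co-primary endpoints is the intent-to-treat analysis set". SAP 4.1.1 adds: "The ITT analysis set is defined as all enrolled subjects (randomized to treatment) and will be analyzed by treatment assigned at randomization".

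**Set actually tested.** Protocol 2.8 takes "randomized subjects with valid MRI core lab data at screening and an appropriate follow-up". SAP 4.3.2 describes the same sample, and both documents add a second route: "as well as randomized subjects who experience a confirmed recurrent event through 24 months regardless of MRI data status". The denominator is the number of evaluable subjects, responders plus nonresponders.

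**Sensitivity analyses.** SAP 4.10 requires, as a minimum for both co-primary endpoints, a worst case ("subjects who withdraw or are lost to follow-up considered recurrent events in the test group and censored in the control group") and its mirror-image best case. A third analysis is conditional: "if necessary, a tipping point analysis (threshold of successes vs. failures between the treatment groups at which the primary test conclusion changes". Under Protocol 3.18, lost to follow-up means that "the subject has missed two consecutive follow-up visits, and the Investigator has documented three failed attempts to contact the subject".

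**Imaging.** SAP 3.6 has the core lab provide "centralized assessment of study endpoints from protocol-required MRI and CT imagery". Protocol 3.5 also has it compare CT as well as MRI scans to determine endpoints. SAP 2.5.1 and 4.3.2 word the responder and nonresponder definitions in terms of MRI only.

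**The concern.** The two set definitions cannot both describe the same co-primary test. In the sample that is used, a subject without valid core-lab imaging counts if a recurrent event is confirmed and is left out if event-free. Such a subject can therefore enter as a responder but never as a nonresponder.

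That would matter less if a required analysis showed how far the result depends on the omitted subjects. None does. A subject who keeps attending, has no event and lacks a usable screening or 24-month scan has neither withdrawn nor been lost under Protocol 3.18, so the worst and best cases do not touch them. Censoring also has no meaning for a binomial proportion. The tipping point is worded in binary terms, but it is optional and its coverage is not stated. The per-protocol and as-treated sets (SAP 4.1.2, 4.1.3) select on treatment, not imaging.

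At stake is a co-primary endpoint on which SAP 4.3.2 allows a stand-alone conclusion of benefit. A missing-data method chosen after the data are seen would be less credible.

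**Working it through.** The readable documents give no brain infarct rate, imaging-loss rate or power for this endpoint, so there is no plan figure to reproduce.

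**Inputs from the documents:** 443 test and 221 control (Protocol 3.3); the unpooled z of SAP 4.3.2; one-sided 0.025, used here without the multiplicity adjustment. The 8% clinical rate is 100% minus the 92% event-free assumption of SAP 2.7.1.

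**Assumed:** clinical rate s and silent-only rate q of 5% + 5%, or 8% + 4%; share m without usable imaging, unrelated to silent infarct; share f of those subjects' clinical events that are confirmed. I take f = 1, then f = 0.5, because an unscanned TIA cannot be confirmed under Protocol 2.3 and events in dropouts may go unseen.

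**Step 1, reported proportion.**

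Reported = [s(1−m) + s·m·f + q(1−m)] / [s(1−m) + s·m·f + (1−s)(1−m)]

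With m = 0.10 and f = 1:
- 5% + 5%: (0.045 + 0.005 + 0.045) / (0.050 + 0.855) = 0.095/0.905 = 10.5%, true 10%.
- 8% + 4%: (0.080 + 0.036) / (0.080 + 0.828) = 0.116/0.908 = 12.8%, true 12%.

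With m = 0.20 the values are 0.090/0.810 = 11.1% and 0.112/0.816 = 13.7%. So 10% loss in test and 20% in control creates a spurious difference of about 0.6 or 0.9 to 1.0 percentage points in favour of the device. Equal loss creates none.

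**Step 2, type I error.** No true arm difference, 1,000,000 simulated trials per row, reject if z > 1.960:

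| Loss, test / control | f | 5% + 5% | 8% + 4% |
|---|---|---|---|
| 0% / 0% | – | 2.0% | 2.0% |
| 10% / 10% | 1 | 2.0% | 2.0% |
| 5% / 10% | 1 | 2.5% | 2.8% |
| 10% / 15% | 1 | 2.5% | 2.9% |
| 10% / 20% | 1 | 3.2% | 4.1% |
| 20% / 10% | 1 | 1.2% | 0.9% |
| 10% / 20% | 0.5 | 2.5% | 2.9% |
| 20% / 10% | 0.5 | 1.5% | 1.4% |

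The no-loss value is about 2.0%, below the nominal 2.5%, so shifts should be read from 2.0%.

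**Step 3, an all-randomized estimate.** Combine the clinical rate in everyone with the silent rate among scanned event-free subjects: ŝ + (1 − ŝ) × (silent / scanned event-free), with a delta-method variance. At 10% / 20% loss and f = 1 it returns 10.0% and 12.0% in both arms, with type I error of 1.9% and 2.0%.

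**Step 4, how a conclusion could turn.** Ten percent loss with s = 5% omits 664 × 0.10 × 0.95 = 63 event-free subjects: 42 test and 21 control. Suppose 21/401 (5.2%) test against 24/200 (12.0%) control, z = 2.65. Restore all subjects, with none of the 21 controls a responder:
- 6 of 42 test subjects responders: 27/443 against 24/221, z = 2.00.
- 7 of 42: 28/443 against 24/221, z = 1.90.
- All 42 (full worst case): 63/443 against 24/221, z about −1.3.

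About 2 of 42 would be expected at a 5% silent rate (42 × 0.05 = 2.1). Seven is a threshold, not a forecast.

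**The case against.** The strongest reply is that this is largely labelling. SAP 4.3.2 says openly who is evaluable, the specific section governs this endpoint, and nothing in it departs from analysis by assigned arm. Counting confirmed events without a scan follows the endpoint definition, which includes clinical stroke, and discarding known strokes would be worse. This stands: including those events is not the fault. But SAP 4.1.1 fixes who is in the set as well as how they are grouped, and relabelling alone would not examine the omitted subjects.

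Loss may also be small. A 24-month MRI is required in both arms (Protocol 3.12, 3.14), and a missing test that may affect the primary endpoint is listed as a violation (Protocol 5.1.1). SAP 4.10 sets a minimum, so further analyses are possible. These points limit the likely size; they do not make any analysis of these subjects required.

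The figures are modest as well. A 5-point difference in loss gives 2.5% to 2.9% against a nominal 2.5%, and seven or more responders among 42 has a probability of only about 0.4% at a 5% silent rate. Both are fair.

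A reader might also infer that CT-only subjects have no route to classification. The documents do not support that: Protocol 3.5 and SAP 3.6 provide for core-lab CT reads in determining endpoints. What remains is a wording mismatch with the MRI-only definitions.

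**Conclusion.** The inconsistency between SAP 4.1/4.1.1 and SAP 4.3.2/Protocol 2.8 is real, and no required analysis covers followed, event-free subjects without usable imaging.

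If loss is unrelated to silent infarct, both arm proportions are overstated. Type I error is then unaffected by equal loss and moves in either direction if loss differs by arm: from about 2.0% to 3.2% to 4.1% at 10% test / 20% control (2.5% to 2.9% if half of unscanned subjects' events are confirmed), or to about 0.9% to 1.2% at 20% / 10%. If loss is related to silent infarct differently by arm, the test can shift even with equal loss rates.

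A reader might infer that the planned test is biased towards the device. The documents do not support that. They give no readable loss rate or direction, and every loss and infarct rate above is an assumption except the 8% clinical rate, which is itself a planning value. This is a risk the plan leaves unexamined, not a demonstrated bias.

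**What to change.** 1. In SAP 4.1 and 4.3.2 and Protocol 2.8, name the brain infarct sample an evaluable (modified ITT) set. Add one pre-specified companion analysis of all randomized subjects by assigned arm that handles missing imaging. The combined estimate in Step 3 or multiple imputation would serve. The Step 3 estimate needs clinical events to be seen in everyone: at 10% loss with half of unscanned subjects' events missed, ŝ = 0.045 + 0.0025 = 0.0475 and the estimate is 0.0475 + 0.9525 × (0.05/0.95) = 9.8%, not 10%. State that assumption.
2. In SAP 4.10, restate the worst and best cases for this endpoint as responder or nonresponder. Make the tipping-point analysis mandatory over every randomized subject without a usable endpoint scan or confirmed event, including those still followed. Treat the tipping point as the main sensitivity analysis and the worst and best cases as bounds, because the full worst case is nearly uninformative (Step 4).
3. Wording only: align the MRI-only responder and nonresponder definitions in SAP 2.5.1 and 4.3.2 with the CT provision in Protocol 3.5 and SAP 3.6.

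The cost is SAP and protocol wording and one extra analysis program, with no new visits or scans; the planned primary test is unchanged. The downside is that the companion estimate may be less favourable than the evaluable-set result.
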